- cc. Only applicable to participants who are enrolled at a site with an on site Fibroscan device. A Fibroscan assessment will only be done at baseline if it was not done at screening.
- dd. HBcrAg and HBV RNA samples may be batched and only selected samples may be tested at the sponsor's request. Samples can be used for assessment of other serologic/virologic markers of HBV.
- ee. Samples may be sequenced based on the sponsor virologist's request, considering the HBV DNA levels. In case of a virologic flare, additional samples for viral sequencing may be taken
- ff. Exploratory serology samples may be analyzed at the sponsor's discretion. Samples may be used to assess virologic or serologic markers of HBV.
- gg. All participants will have sparse PK sampling for JNJ 3989, NA, and PegIFN α2a. Bioanalysis of NA and PegIFN α2a is optional at the discretion of the sponsor. Bioanalysis of JNJ 6379 may also be done on samples collected from participants who received JNJ 6379 up to Protocol Amendment 5.
  For all samples, the date and time of the preceding 2 intakes of NA, the date and time of the previous JNJ 3989 administration, the date and time of the previous PegIFN α2a administration (if applicable), and the date and time of PK sampling should be recorded.
- hh. One sample at any time between 2 and 8 hours after JNJ 3989 dosing. Before leaving the study site, the participant's well being should be confirmed.
- ii. All participants who consent to participate in the intensive PK substudy (optional) will undergo intensive PK sampling at Week 24. If necessary (eg, for operational reasons), this visit may be scheduled at Week 28 or 32. The study intervention should be taken on site and time of dosing should be recorded. Pharmacokinetic samples will be taken predose and 15 minutes, 30 minutes, 1, 2, 3, 4, 6, 8,\* 10,\* and 24 hours post JNJ 3989 dose (\*the 8 and 10 hours postdose samples are optional). All efforts will be made to obtain the PK samples at the exact nominal time relative to dosing. However, samples obtained within 20% of the nominal time from dosing (eg, +/ 12 minutes of a 60 minute time point) will not be captured as a protocol deviation if the exact time of the sample collection is noted on the source document and data collection record (eg, CRF).
- ii. Sparse PK sampling is not required for participant with intensive PK sampling at the same visit.

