Study Phase	Open-label Consolidation Phase						Follow-up a,b													
Consolidation (C)/ Follow up (FU) Week (W)	C W2	C W4	C W6	C W8	C W12 / EOSI / WD°	FU W2	FU W4	FU W8 d	FU W12	FU W16 d	FU W20 d	FU W24	FU W28 d	FU W32 d	FU W36	FU W40 d	FU W44 d	FU W48 / EOS		
C / FU Study Day (Window)	15 +/ 3d	29 +/ 3d	43 +/ 3d	57 +/ 3d	85 +/ 3d	15 +/ 4d	29 +/ 4d	57 +/ 4d	85 +/ 4d	113 +/ 4d	141 +/ 4d	169 +/ 4d	197 +/ 4d	225 +/ 4d	253 +/ 4d	281 +/ 4d	309 +/ 4d	337 +/ 4d		
Urinalysis r		X		X	X	X t	(X)	(X)	(X)	(X)	(X)	(X)	(X)	(X)	(X)	(X)	(X)	X		
Urine chemistry s		X		X	X	X t	(X)	(X)	(X)	(X)	(X)	(X)	(X)	(X)	(X)	(X)	(X)	X		
Urine pregnancy test (women of childbearing potential only)		X		X	X		X v	X	X v	X v	X v	X v	X v	X v	X v	X v	X v	х		
AFP test p,u					X							X						X		
TSH and T4					X															
Efficacy Evaluations																				
Fibroscan w					(X)							(X)						(X)		
HBV Virology																				
Blood sampling for HBV DNAkk	X	X	X	X	X	X	X	X	X	X	X	X	X	X	X	X	X	X		
Blood sampling for HBV RNA x		X		X	X	X	X	X	X	X	X	X	X	X	X	X	X	X		
Sampling for viral genome sequencing y		X			X		X		X		X		X	X		X		X		
HBV Serology																				
Blood sampling for:																				
Anti HBs and anti HBe					X		X		X			X			X			X		
HBsAg and HBeAg (qualitative)					X				X			X						X		
HBsAg (quantitative)	X	X	X	X	X	X	X	X	X	X	X	X	X	X	X	X	X	X		
HBeAg (quantitative)	X	X	X	X	X	X	X	X	X	X	X	X	X	X	X	X	X	X		
HBcrAg x		X			X		X		X			X			X			X		
Exploratory serology 		X			X	X	X	X	X	X	X	X			X			X		
Clinical Pharmacology Assessments																				
Blood sampling for sparse PK of JNJ 3989, PegIFN α2a and NA aa		Xbb		X bb,e e	(X)cc															
Blood sampling for intensive PK of JNJ 3989, PegIFN α2a and NA (PK substudy) dd				X																
Exploratory Host Biomarkers																				
Whole blood RNA gene expression		X			X							X						X		
Whole blood single cell profiling		X			X	X	X	X	X	X		X			X			X		
Host serum proteins (eg, cytokines)		X			X		X	X	X	X		X			X			X		
Antidrug antibodies (to JNJ 3989 and PegIFN α2a)		X		X	X		X		X			X						X		

CONFIDENTIAL – FOIA Exemptions Apply in U.S. Status: Approved, Date: 25 November 2021

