#### The discontinuation criteria are:

- The participant withdraws consent to receive study intervention.
- The investigator believes that for safety or tolerability reasons (eg, AE) it is in the best interest of the participant to discontinue JNJ-3989 and PegIFN- $\alpha$ 2a.
- The participant becomes pregnant.
- The participant has a ≥grade 3 rash or allergic reaction.
- The participant has signs of hepatic decompensation (ie, clinical evidence of ascites, bleeding varices, or hepatic encephalopathy) or an increase in direct bilirubin >1.5x ULN in combination with INR ≥1.5x ULN or albumin <3.0 g/dL. Treatment with JNJ-3989 should be discontinued and alternative treatment options (outside the study) should be considered in discussion with the Sponsor.
- The participant has a confirmed ≥grade 3 eGFRcr abnormality.
  - If eGFRcr is not confirmed by eGFRcys, or not considered at least possibly related to JNJ-3989 or PegIFN- $\alpha$ 2a, or resolved after changing tenofovir disoproxil to TAF (if the patient was receiving tenofovir disoproxil), treatment with JNJ-3989 or PegIFN- $\alpha$ 2a can be continued after discussion with the sponsor.
- The participant has a QTcF prolongation (defined as a QTcF value of >500 ms, or an increase from baseline of >60 ms) at any given time point.
- The participant requires ≥7 days of treatment with any of the disallowed medications listed in Section 6.5 and does not intend to discontinue treatment with the disallowed medication.
- The participant has confirmed HBV virologic breakthrough (ie, confirmed on-treatment HBV DNA increase by >1 log10 IU/mL from nadir or confirmed on-treatment HBV DNA level >200 IU/mL in participants who had HBV DNA level <LLOQ of the HBV DNA assay). In case of virologic breakthrough, the same assessments will be done at an unscheduled visit as will be done in case of an ALT flare, but no PBMC sample will be taken (see Section 8.3.6.2 and Schedule of Activities).

If virologic breakthrough occurs during JNJ-3989 and PegIFN- $\alpha$ 2a administration, this does not automatically lead to stop of JNJ-3989 and/or PegIFN- $\alpha$ 2a, but should be assessed/discussed with the Sponsor.

In case of virologic breakthrough, a viral sequencing sample will be collected at the next visit.

- The participant has ALT/AST elevations, as described in Section 8.3.6.2, Intervention-emergent ALT/AST Elevations.

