### 5.3.1.1.8. Virologic Breakthrough

HBV virological breakthrough is defined as having a confirmed on-treatment HBV DNA increase by  $>1 \log_{10}$  from nadir level (lowest level reached) in participants who didn't have on-treatment HBV DNA level below the lower limit of quantification (LLOQ) or a confirmed on-treatment HBV DNA level  $>200$  IU/mL in participants who had on-treatment HBV DNA level below the lower limit of quantification (LLOQ). Confirmed HBV DNA increase/level means that the criterion should be fulfilled at 2 or more consecutive time points or at the last observed on-treatment time point. On-treatment will be defined as the time period in which the participant receives any of the study interventions (including NA).

In addition, participants who experience a virologic breakthrough followed by on-treatment biochemical flare will be evaluated.

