### 7.1. Time Points and Samples

When analyzing sequencing data, the focus will be on genetic variants at

- Time Point of Sequence at Baseline (BLSEQ): Last available pre-first dose time point in the study with sequence data available
- Time Point of Sequence at End of Study Agent (last available on-treatment time point, with a specific focus on subjects not meeting the NA treatment completion criteria)
- Time Point of Sequence at Virologic Breakthrough: time point with sequence data available closest to the time point of virologic breakthrough (FTPT) (See Section 5.3.1.1.8 for virologic breakthrough definition)
- Time Point of Sequence at Virologic Flare: time point with sequence data available closest to the time point of Virologic flare (See Section 5.3.1.1.9 for virologic flare definition)
- Time Point of Sequence at End of Study (ESSEQ): last available off-treatment post-baseline time point in the study with sequence data available
- Time Point of Sequence at Re-treatment during Post-treatment Follow-up: time point with sequence data available closest to time point where re-treatment criteria is met (See Section 5.3.1.1.2.2)
- Aggregated Post-Baseline Study Period (ASSEQ): entire post-baseline study period, aggregate of all available time points in the study with sequence data available
- Aggregated Post-Baseline Treatment Period (ATSEQ): entire post-baseline treatment period, aggregate of all available post-baseline time points during the treatment phase with sequence data available
- Aggregated Off-treatment follow-up period: entire period with no drug taken, aggregate of all available time points during the off-treatment period with sequence data available

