### 7.5.2. Post-Baseline

- Time of Virologic Breakthrough (if applicable)

For subjects with virologic breakthrough, the incidence of treatment emergent (NGS) and treatment enriched genetic variations (with primary focus on substitutions) will be tabulated in frequency outputs (n, %) and the genetic variations will be listed for all subjects with paired baseline and post-baseline sequencing data.

The return to baseline for subjects with virologic breakthrough and treatment-emergent genetic variations at time of virologic breakthrough may be tabulated in frequency outputs based on NGS data, as well as the treatment-emergent genetic variations in subjects who did not return to baseline.

- Time of End of Treatment

For subjects who don't meet the NA treatment completion criteria, the incidence of treatment emergent and treatment enriched variants (with primary focus on substitutions) will be tabulated

in frequency outputs (n, %) and the genetic variations will be listed for all subjects with paired baseline and post-baseline sequencing data.

The return to baseline for subjects who don't meet the NA treatment completion criteria and treatment-emergent genetic variations end of treatment may be tabulated in frequency outputs based on NGS data, as well as the treatment-emergent genetic variations in subjects who did not return to baseline.

- Time of Virologic /Clinical Flare (if applicable)

For subjects with virologic/clinical flare, the incidence of treatment emergent (NGS) and treatment enriched genetic variations (with primary focus on substitutions) will be tabulated in frequency outputs (n, %) and the genetic variations will be listed for all subjects with paired baseline and post-baseline sequencing data.

The return to baseline for subjects with virologic/clinical flare and treatment-emergent genetic variations at time of virologic/clinical flare may be tabulated in frequency outputs based on NGS data, as well as the treatment-emergent genetic variations in subjects who did not return to baseline.

- Time of Re-treatment during Post-treatment Follow-up (if applicable)

For subjects who meet re-treatment criteria during follow-up, the incidence of treatment emergent and treatment enriched variants (with primary focus on substitutions) will be tabulated in frequency outputs (n, %) and the genetic variations will be listed for all subjects with paired baseline and post-baseline sequencing data.

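### SAP 7.1 takes the sequence at virologic breakthrough as the nearest sequenced sample in time, so a pre-breakthrough sample can enter the breakthrough tables

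*SAP*

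**What the plan says.** SAP 7.1 (Time Points and Samples) sets the breakthrough sequence as the "time point with sequence data available closest to the time point of virologic breakthrough (FTPT"). Confirmation is defined in SAP 5.3.1.1.8: "the criterion should be fulfilled at 2 or more consecutive time points or at the last observed on-treatment time point". Neither section says which of the qualifying time points is FTPT.

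Protocol 7.1 (Discontinuation of Study Intervention) provides a dedicated sample: "In case of virologic breakthrough, a viral sequencing sample will be collected at the next visit". It also says that "the same assessments will be done at an unscheduled visit as will be done in case of an ALT flare".

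Routine samples are in the row "Sampling for viral genome sequencing" of the Schedules of Activities (Protocol 1.3.1 and 1.3.2). HBV DNA is measured at every treatment visit; sequencing samples are taken at fewer. A sample counts under SAP 7.1 only if it has sequence data, and the schedule notes that "Samples may be sequenced based on the sponsor virologist's request, considering the HBV DNA levels".

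The chosen sample feeds SAP 7.5.2: "For subjects with virologic breakthrough, the incidence of treatment emergent (NGS) and treatment enriched genetic variations" are to be tabulated as n and %, with a possible follow-on table of return to baseline.

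**The concern.** Elsewhere in the SAP 7.1 list, baseline, end of study agent and end of study each have a directed rule (the last available sample of a stated kind). The breakthrough rule has none. Read literally, nearest in time allows a sample from before HBV DNA rose.

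Under SAP 7.2 an emerging variant must be below 1% at baseline and at least 15% at the later time point. If variants are selected as HBV DNA rises, a sample taken before the rise will tend to lower the count or leave it unchanged. The participants concerned are those in whom resistance is the question. For them, the choice of sample would rest on visit-day variation and not on a stated rule.

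**Working it through.** The plan gives no figure to reproduce. The check counts how often the rule can select an earlier sample.

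**Inputs (Protocol 1.3.1 and 1.3.2)**
- Post-baseline treatment visits with HBV DNA: W2, 4, 6, 8, 12, 16, 20, 24, 28, 32, 36 (11) and C W2, 4, 6, 8, 12 (5). Total 16.
- Routine sequencing samples among these: W4, 12, 20, 32, 36, C W4, C W12. Total 7.
- Visits without a routine sample: 16 − 7 = 9.
- Visit windows: ±2 days to W12, ±3 days after that.

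**Assumptions for the main case:** FTPT is the visit where the rise is first seen; the extra sample is at the next scheduled visit; both samples yield sequence data; the baseline sample is not eligible, because emergence is measured against it.

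**Step 1: nominal gaps at the 9 visits (weeks)**

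| First seen | Previous sample (gap) | Next-visit sample (gap) | Nearest |
|---|---|---|---|
| W2 | none after baseline | W4 (2) | later |
| W6 | W4 (2) | W8 (2) | tie |
| W8 | W4 (4) | W12 (4) | tie |
| W16 | W12 (4) | W20 (4) | tie |
| W24 | W20 (4) | W28 (4) | tie |
| W28 | W20 (8) | W32 (4) | later |
| C W2 | W36 (2) | C W4 (2) | tie |
| C W6 | C W4 (2) | C W8 (2) | tie |
| C W8 | C W4 (4) | C W12 (4) | tie |

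Seven visits tie, 2 select the later sample, and the other 7 have a same-visit sample.

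**Step 2: breaking the ties.** Let j1, j0 and j2 be the day shifts of the earlier, breakthrough and later visits. With common nominal gap g, the earlier gap is g + j0 − j1 and the later gap is g + j2 − j0. The earlier sample is nearer when 2·j0 < j1 + j2.
- Shifts uniform on −3..3: 7³ = 343 combinations. Exact ties need j1 and j2 of equal parity: 4×4 + 3×3 = 25 (7.3%). By symmetry the earlier sample is nearer in (343 − 25)/2 = 159, and 159/343 = 0.464.
- Shifts uniform on −2..2: 5³ = 125; exact ties 2×2 + 3×3 = 13 (10.4%); (125 − 13)/2 = 56, and 56/125 = 0.448.

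Across all 16 visits, with onset equally likely at each: 7 × 0.464 / 16 = 0.203.

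**Step 3: sensitivity to when the extra sample is taken (nominal days, number of the 16 visits)**

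| Extra sample taken | Same visit | Tie | Strictly earlier | Later |
|---|---|---|---|---|
| Next scheduled visit after onset | 7 | 7 | 0 | 2 |
| One visit after confirmation | 7 | 4 | 3 | 2 |
| Unscheduled visit about 1 week after onset (assumed) | 7 | 0 | 0 | 9 |

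The 3 strictly earlier cases are W6 (W4 at 2 weeks against W12 at 6), W24 (W20 at 4 against W32 at 8) and C W6 (C W4 at 2 against C W12 at 6).

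**The case against.** **The variants are not lost.** A reader might infer that emergent variants go undetected. The documents do not support that. SAP 7.1 also defines aggregates over the treatment period and over the whole study. SAP 7.3 asks for emergent and enriched substitutions at the post-baseline time points in 7.1, and SAP 7.5.3 lists aggregate sequence data for all subjects. A variant in the later sample appears there. What remains is an undercount in the breakthrough tables and the return-to-baseline follow-on, which the aggregates do not repair.

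**The extra sample may be early.** The unscheduled visit mirrors the ALT-flare visit, which Protocol 8.3.6.2 places preferably within 7 days of receiving results. If that is the next visit, the problem disappears. But the laboratory tests listed there do not include sequencing, and the protocol does not say that the two visits are the same.

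**The earlier sample may not be sequenceable.** This is true for some participants whose HBV DNA was below the LLOQ (20 IU/mL) before rising above 200 IU/mL. The sequencing limit is not given. The other arm of the definition covers participants who never fell below the LLOQ.

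**A tie rule exists.** SAP 2.1.3 prefers the later of two equidistant measurements, but for Table 2 target days, with no link to 7.1. Even if borrowed, it settles only exact ties (7.3% of the ±3-day combinations).

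**The tables may not be produced.** SAP 7.5 requires at least 5 participants with paired sequence data, and the breakthrough output is marked as if applicable. This stands and limits the practical weight.

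**Flare and re-treatment.** A reader might extend the point to these because their wording is similar, for example "time point with sequence data available closest to time point where re-treatment criteria is met". That extension is not supported. Protocol 1.3.2 already provides a sequencing sample at the visit confirming a virologic flare. SAP Amendment 4 records that only one participant met the completion criteria and stopped NA. The confirmed HBV DNA re-treatment criteria need values at least 4 weeks apart, so a relevant sample can precede the date they are met, and a forward-only rule could select one taken after NA restart.

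**Conclusion.** The point holds as a minor specification gap in one exploratory, descriptive analysis. As written, SAP 7.1 can place a pre-breakthrough sample in the breakthrough tables.

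The size depends mainly on when the extra sample is taken. With it at the next scheduled visit and both samples sequenced, the figures are about 46% at the 7 tied visits and about 20% over all 16, the latter with onset equally likely at each visit. The 46% should not be read as the share of all breakthroughs. If the extra sample comes about one week after onset, no visit selects an earlier sample. If it follows confirmation by a visit, 3 of 16 select an earlier sample outright, with 4 further ties.

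The primary endpoint and sample size are unaffected.

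**What to change.** In SAP 7.1, for virologic breakthrough only:
- Define FTPT as the first time point meeting the criterion that is later confirmed.
- Use the first time point with sequence data on or after FTPT, up to and including the protocol's post-breakthrough sample.
- If there is none, list the nearest earlier sample with a flag, and leave it out of the at-breakthrough frequency of emergent and enriched variants.

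With all samples sequenced, no earlier sample could then be selected at any of the 16 visits: 7 would use the same-visit sample and 9 a later one. The upper bound stops the forward search from running past the sample the protocol intends.

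The cost is SAP wording, with no new samples. The downside is that a few participants may appear only in the listing, which could take the table below the output threshold of 5 participants. Leave the flare and re-treatment rules as they are.

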## 7.2. Definitions

(Baseline) Genetic variations (i.e., aka baseline polymorphisms) are defined as changes (on the amino acid or nucleotide level) in the subject viral sequence compared to a HBV genotype specific reference viral sequence and/or the universal HBV reference sequence (NCBI ID X02763). The reference sequence to be used is provided in the database. The reference viral sequences to be used are:

Virus	Genotype	NCBI genbank accession	NGS isolate name	Sanger genbank accession	Sanger isolate name
HBV	A	X02763	adw2	X02763	adw2
HBV	B	AB219428	PNN3	D00329	pJDW233
HBV	C	GQ924620	M38	AB014362	03D03HCC
HBV	D	AF121240	11066	V01460	ayw
HBV	E	AB106564	GA325	X75657	ayw4
HBV	F	AY090458	70H	X75658	adw4q

Virus	Genotype	NCBI genbank accession	NGS isolate name	Sanger genbank accession	Sanger isolate name
HBV	G	AF160501	IG29227	AB064311	USG825
HBV	H	FJ356716	CL150171	AY090460	LAS2523
HBV	I	EU833891	H4536-07		

**Wild type:** If at certain position the amino acid/nucleotide in the subject sequence matches the reference sequence, that is no genetic variation is present at that position, the virus is considered to be wild type at that position.

**Emerging viral variation:** If at certain position a genetic variation is absent at baseline but present at later time point, the genetic variation is considered to be emerging at that time point. For NGS, emerging will be defined based on the frequency of variant at baseline and at the later time point. “Absent at baseline” is defined as a frequency of variant below 1% (<1%). “Present at later point” is defined as a frequency of variant equal or greater than 15% ( $\geq 15\%$ ) at the later time point.

**Enriched genetic variations:** are exclusively defined for NGS analysis. If at a certain position a genetic variation has a frequency of variant of  $\geq 1\%$  but  $< 15\%$  at baseline and a frequency of variant of  $\geq 15\%$  at a later time point and an increase in read frequency of  $\geq 15\%$ .

### 7.3. Parameters to Analyze

At specified time points and for each list specified in the section below, the following parameters will be analyzed:

- Number (%) of subjects with a substitution at a specific position.
- Number (%) of subjects with a specific substitution.
- Number (%) of subjects with a specific substitution profile
- Number (%) of subjects with substitutions on amino acid level (overall and by HBV genotype (A, B, C, D, E, F, G, H, I, J and Unknown))
  - at positions of interest in the major hydrophilic loop of HBsAg.
- Number (%) of subjects with substitutions on nucleotide level
  - at the binding site positions of JNJ-3989 (i.e., JNJ-3976 and JNJ-3924) (overall and by HBV genotype (A, B, C, D, E, F, G, H, I, J and Unknown)).
  - in the precore (genome position 1896) and basal core promotor (genome positions 1762/1764) region (overall, by HBV genotype (A, B, C, D, E, F, G, H, I, J and Unknown) and by baseline HBeAg status)
- Number (%) of subjects with treatment-emergent and enriched substitutions on amino acid level at post-baseline time points (as defined in Section 7.1) by substitution profile
  - at HBV core protein position of interest (list of 15 POI),
  - at positions of interest in the polymerase region,

- Number (%) of subjects with treatment-emergent and treatment-enriched substitutions on nucleotide level at post-baseline time points (as defined in Section 7.1) by substitution profile
  - at the binding site positions of JNJ-3989 (overall and by HBV genotype (A, B, C, D, E, F, G, H, I and J)).

The focus will be on substitutions at a time point, emerging and enriched variations and reversion to wild type or baseline state. The above summaries will be repeated for genetic variations (not needed for CSR).

In the sequence analysis, sequences will be mapped to the respective genotype specific reference sequences after which nt changes and aa substitutions will be annotated compared to the respective genotype specific reference (see Table in Section 7.2). In addition, the X02763 (HBV genotype A), which is the master reference sequence of the HBV db, will be used as universal reference sequence. Focus of analysis and reporting of results will be on comparison versus Universal reference sequence

All NGS data will be collected using a nt and aa read frequency cut-off of  $\geq 0.01$ . For the analysis of baseline nt changes and/or aa substitutions in terms of frequency of variant and impact on treatment outcome, a read frequency cut-off of  $\geq 0.15$  will be used. The analysis of treatment-emergent nt changes or aa substitutions will consider nt changes or aa substitutions absent at baseline ( $<0.01$  read frequency) but present at a read frequency of  $\geq 0.15$  at later time points. Virology analyses based on NGS data will also evaluate treatment-enriched nt changes and aa substitutions, defined as present at baseline with a read frequency  $\geq 0.01$  but  $<0.15$  and with an increase in read frequency of at least 0.15 post-baseline. A minimum increase in read frequency of 0.15 compared to baseline excludes small, potentially technical variations in the read frequency of minority nt changes and aa substitutions which are not expected to have clinical relevance. In addition, for subjects with treatment failure nt changes and aa substitutions detected with a read frequency  $\geq 0.01$  at baseline, at time of failure and at end of study will be described in a listing. The persistence of treatment-emergent nt changes and aa substitutions will be evaluated using a cut-off of  $\geq 0.15$  and  $\geq 0.01$ .

The applicability of the sequencing approach described here (e.g., the 0.01 sensitivity limit) will be assessed during the development program and might be adapted if needed.

